As part of this objective, we will conduct individual interviews with VA and ADNA coordinators from 16 purposefully selected VA medical centers with recently established and existing VD-HCBS programs. The 32 coordinators will include 16 ADNA Coordinators and 16 VA coordinators from 16 VD-HCBS program sites. Whenever possible, each coordinator will be interviewed at two time points (64 total interviews). The first set of interviews with the coordinators, will be 2 to 4 months after GEC allows the program to begin enrolling Veterans (completion of the Lewin Group readiness review). The second set of interviews will be 6 months after the initial interview to obtain follow-up data about implementation process, compared to the initial startup time, implementation strategies that they have employed, and their evaluation of implementation success (See Interview Guides). If it is not possible to interview sites at 2months after GEC allowed to begin enrolling Veterans (completion of the Lewin Group readiness review), we will conduct one interview at least 6-months after readiness review. From the VA coordinators, we will request a local VAMC leader (n=16) and a VISN GEC leader (n=16) for one-time interviews (32 interviews). Additionally, we will ask the GEC VISN leads when we interview them to recommend local GEC contacts. Pair Interview Dropout. Our primary interest is in triangulating data from the VA and ADNA coordinators at a case level. However, there will be dropout and turnover in the coordinator positions. When there is dropout, we will seek to recruit another individual from the site to complete the pairwise analysis. If this is not possible, we will exclude that program site in the case-level analysis and continue to recruit until we have 16 program sites, with participation from both the VA and ADNA coordinators. We anticipate dropout of 25% in the pairwise analysis and are requesting permission to perform additional interviews at 4 sites (8 interviews)

Including the additional interviews to allow for the projected drop out rate, we estimate that a Total of 104 interviews will be conducted with a total of 72 individuals.

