## **Recruitment Methods:**

We will purposefully select 16 VAMCs based on criteria related to quality of VA-ADNA collaboration and standard practice, identified as factors impacting implementation in our prior evaluations. For each case, we will conduct individual interviews with VA VD-HCBS coordinators and associated ADNA coordinators plus additional key decision makers identified by coordinators and GEC points-of-contact for the VISNs that cover the VD-HCBS programs in our sample. Coordinators will be those reported by The Lewin Group, the contractor responsible for Technical Assistance, as the contact person for the VD-HCBS program. Additional respondents will be identified when coordinators are asked to name their local VAMC leader and a VISN GEC leader as described above. Once potential participants have been identified within eligible VAMCs and ADNAs, they will be sent an introductory letter to their work email address. The letter will inform them about the interview, the goal of the interview, that the interview will be recorded for transcription purposes only, that they may contact a Providence-based project staff member to address any questions or concerns they may have prior to participating or to schedule an interview, and that unless a refusal is received they will be contacted at their work telephone number a week after the email is sent to schedule an interview. Participants will also be informed that they may be required to do this interview on offduty time unless their supervisor approves on-duty time. If they are willing to participate, a phone call will be scheduled.

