## **Objective 3:**

*Analysis* - Our primary unit of analysis for this implementation evaluation will be the VA-ADNA *institutional pairs* implementing this program. Thus, this will be a case-oriented analysis. Below we describe a three-stage team approach to analyze data, adapted from Damschroder and we will repeat these stages at each of the two data collection phases, ultimately integrating data at case-level to describe program implementation from two to eight months after randomization.

*Coding* - First, open-ended data from the interviews will be reviewed and coded by a team of two researchers. They will code transcribed data according to CFIR and ERIC constructs using directed content analysis, in which codes are developed *a priori*; additional data derived codes will be established for text that cannot be coded with the *a priori* codes. Thus, this will be primarily a deductive approach, and we will additionally create codes that are inductively derived from data. The researchers will first independently read through a subset of interviews (about three to five) to apply initial codes and then come together to compare codes and arrive at agreement through deliberation and consensus. The researchers will then develop a final list of codes and apply these codes to all responses.

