Memos- Researchers will aggregate individual interviews from VA and ADNA key informants into case memos and identify whether CFIR constructs are manifested as facilitators or barriers and what implementation strategies are used. A case memo is a Word document in which quotes from individual interviews within each case are collated and organized by construct. To determine whether CFIR constructs manifest as facilitators or barriers, researchers will independently rate coded text according to strength and valence on a 5 point scale, with -2 reflecting a statement about a strong barrier to +2 reflecting a statement about a strong facilitator. They will again use a team approach to resolve differences through deliberation and discussion and arrive at final, agreed upon ratings. An overall rating for each construct will be established based on average of ratings for individual quotes under that construct. The memos will also include a summary statement to describe what was coded (e.g., how did key informants describe the innovation source) and whether implementation context or strategy can be ascribed to a specific entity (i.e., solely VA or ADNA) or if it is a shared strategy, and they will include a rationale for ratings (e.g., the program was mandated without buy-in from local entities, thus a strong negative rating). We will build on the case memos developed during the first data collection period with data from the second to describe implementation strategies and any updates from the first interview for cases that have two interviews.

Qualitative Comparative Analysis - The objective of this stage will be to consolidate collected implementation data to assess how combinations of strategies and barriers relate to outcomes using Qualitative Comparative Analysis (QCA). At the individual level, outcomes will be high report of unmet needs for personal care or very good to excellent satisfaction, analyzed as part of Objective1 and, for use in QCA, transformed to reflect presence or absence of these values. At the institutional level, outcomes will be the number of Veterans receiving care through VDHCBS as a proportion of the total number of Veterans receiving Home and Community Based Care one year after program start. QCA is a

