quantitative, case-oriented method that uses applied set theory and Boolean algebra to examine multifactorial causality (i.e., when several variables together have a joint effect on an outcome). In essence, it offers a systematic way to compare cases for factors related to success of an outcome, distinguishing between necessary and sufficient conditions, in projects with small or medium-N. It is a well-established quantitative approach that has been in use since the 1980s, especially in political science, to answer research questions like "What combinations of conditions are directly connected to the outcome of interest, such that cases with those specific combinations also always had the outcome present?" Although quantitative, QCA is a form of case-oriented research that requires close familiarity with the gualitative dataset of interest and theoretical framework to interpret results. As Baptist and Befani say in their primer on QCA, "Put simply, QCA allows evaluators to answer the question 'what works best, why, and under what circumstances' quite literally, in a way that emerges directly from other empirical analysis; that can be replicated by other researchers, and is generalizable to other contexts." Because findings from QCA will be generalizable, even though we will be evaluating a subset of cases, they could be used to inform future expansion of VD-HCBS or assistance for struggling entities.

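### Objective 3 calls its QCA findings generalizable, but 16 purposefully selected sites, an open pool of conditions and no replication or chance check do not support that claim

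*Combined protocol and SAP*

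**What the plan says.** The Objective 3 analysis takes the pair formed by a VA medical center and its aging-network agency as its unit: "Thus, this will be a case-oriented analysis". Under 5.0 Study Procedures, Objective 3, interviews come "from 16 purposefully selected VA medical centers with recently established and existing VD-HCBS programs". Recruitment Methods for that objective adds: "We will purposefully select 16 VAMCs based on criteria related to quality of VA-ADNA collaboration and standard practice". If a pair cannot be completed, "we will exclude that program site in the case-level analysis and continue to recruit until we have 16 program sites", so the analysis stays at 16 cases.

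On conditions, the Coding paragraph of 7.0 says of the two researchers: "They will code transcribed data according to CFIR and ERIC constructs using directed content analysis". It then leaves the list open: "additional data derived codes will be established for text that cannot be coded". Each framework construct gets an averaged rating between -2 and +2. QCA then relates combinations of strategies and barriers to three outcomes: unmet need, satisfaction, and the programme's share of Veterans in home and community-based care.

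The QCA paragraph ends with the claim at issue: "Because findings from QCA will be generalizable, even though we will be evaluating a subset of cases". From this the plan concludes that the findings might guide later expansion or support for sites in difficulty. Its support is a cited primer's general description of the method.

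**The concern.** Generalizability appears as a premise, not as something the study will show. Two separate things would be needed to support it.

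- **A route from the 16 sites to the others.** There is no sampling frame or random selection, and no set of sites is held back for checking. The criteria used to choose sites are ones that the plan itself describes as having affected implementation in earlier evaluations. That is a sound way to pick informative cases, but it gives no basis for saying that a pattern seen in them will hold at the 90 additional sites named in the Introduction.
- **Some assurance that the pattern is not chance.** QCA looks for combinations of conditions under which the outcome is always present. With 16 cases and many possible combinations, some can fit perfectly without any real relation. The plan sets nothing in advance that would limit this or measure it.

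At stake is how a recipe from this analysis is read. It could be taken as an established route to success when the design can offer it only as a lead.

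**Working it through.** The plan states no error rate for QCA, so there is no figure of its own to reproduce. The check asks how often a perfectly consistent recipe would appear if no condition were related to the outcome.

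**Inputs from the documents.** There are 16 cases (5.0, Objective 3) and three outcomes (7.0, Objective 3). Perfect consistency is taken from the example question in the QCA paragraph. It is not a stated threshold.

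**Inputs that the documents do not give, so assumed and varied.** These are the number of candidate conditions k, the number of sites with the outcome m, and the minimum number of covered sites f. Each condition is taken as present at a site with probability 0.5, independently. A recipe is any conjunction of one to three conditions, each either present or absent.

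**Number of candidate recipes.** This is the sum over d = 1, 2, 3 of C(k,d) × 2^d. For k = 4 it is 8 + 24 + 32 = 64.

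**Expected number of spurious recipes, k = 4, f = 3.** A conjunction of d conditions covers a given site with probability r = 1/2^d. It counts if it covers at least 3 of the m sites with the outcome and none of the other 16 − m:

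P(Bin(m, r) ≥ 3) × (1 − r)^(16 − m)

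For m = 8:
- d = 1: 0.8555 × 0.0039 = 0.0033
- d = 2: 0.3215 × 0.1001 = 0.0322
- d = 3: 0.0674 × 0.3436 = 0.0232

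Expected number = 8 × 0.0033 + 24 × 0.0322 + 32 × 0.0232 ≈ 1.54.

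For m = 4 the three probabilities are 0.00008, 0.00161 and 0.00143, and the expected number is about 0.085.

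**Chance of at least one.** Recipes overlap, so this was simulated. Separate runs differ by up to about three percentage points, and ranges are shown where they do.

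| Candidate conditions | Sites with outcome | Minimum covered sites | Chance of at least one spurious recipe |
|---|---|---|---|
| 4 | 4 of 16 | 3 | 6–7% |
| 4 | 5 of 16 | 3 | 13–15% |
| 4 | 8 of 16 | 3 | 59–61% |
| 4 | 11 of 16 | 3 | 96–97% |
| 3 | 8 of 16 | 3 | 35–38% |
| 6 | 8 of 16 | 3 | 89–91% |
| 4 | 8 of 16 | 4 | 24–26% |

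The 6–7% respects its upper bound of 8.5% from the expected number at m = 4.

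**Three outcomes.** If they were independent, 60% for one outcome becomes 1 − 0.40³ = 94% for at least one of three, and 13% becomes 1 − 0.87³ = 34%. The outcomes are probably related, so these are upper guides.

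**Empty rows.** Sixteen cases fill at most 16 truth-table rows. Five conditions give 32 rows, so at least 16 are empty. Six give 64, so at least 48 are empty.

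**The case against.** The strongest reply is that this is case-oriented work, for which purposeful selection is proper and QCA was designed. Coding is mainly deductive, from two published frameworks, and the plan asks for close knowledge of the cases when results are read. A blind search over unrelated random conditions is therefore a severe comparison. This stands as a caution about the percentages. It does not supply the missing link from 16 selected cases to other sites.

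The figures also depend on what is counted. If only complete truth-table rows count, with each site having the outcome with probability 0.5 and at least three cases per row, the chance is 22.4% with three conditions, 12.6% with four and 1.4% with six. It then falls as conditions are added, because cases spread out over more rows. QCA normally reduces rows to shorter conjunctions, so the table above is closer to what would be reported, but the sensitivity is real.

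A reader might infer four stronger things, none of which the documents support:

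- **That a spurious recipe is more likely than not.** This holds in some settings and fails in others, and the plan fixes none of the inputs.
- **That the results will be products of site selection.** The plan does not say that collaboration quality will be a QCA condition, or that only sites with good collaboration are chosen. It seeks a range of contexts and includes both new and existing programmes.
- **That the recipes are bound to drive the expansion.** The plan says only that they might inform it.
- **That conditions will be searched without limit.** No cap is stated, but that is a gap in specification, not evidence of such a search.

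**Conclusion.** The concern holds in this form: the plan claims generalizability for its QCA findings, and neither the selection of sites nor the analysis as described supports the claim. The point about selection needs no calculation. The point about chance has no single size. Under the stated random model with four candidate conditions and at least three covered sites, the chance runs from about 6–7% to 96–97% as the number of sites with the outcome goes from 4 to 11 of 16. That width is the finding: the plan leaves open the quantities that decide it.

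The result rests on independent conditions with prevalence 0.5, on perfect consistency, and on counting conjunctions of up to three conditions. The absence of thresholds and checks is judged on the available text, which lacks some material between the Objectives and the Data Use Agreements.

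**What to change.** 1. Replace the generalizability sentence with a statement that QCA findings are hypotheses, to be checked at expansion sites outside the 16.
2. Before outcome data are merged with the case memos, fix the following: the candidate conditions, the cut-points that turn the averaged ratings and each outcome into set membership, the consistency threshold, and the minimum number of cases per configuration.
3. Report coverage with consistency for every solution.
4. Run a permutation check: shuffle the outcome across the 16 sites, repeat the whole procedure, and report how often an equally consistent solution appears. With 8 of 16 sites there are 16!/(8! × 8!) = 12,870 distinct arrangements, so full enumeration is possible.

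No fixed cap on conditions is needed. A cap of four alone would leave about 60% at 8 of 16 sites with at least three cases, while raising the minimum to four cases brings that to 24–26%. Choose the number of conditions and the minimum together, so that the permutation rate is acceptably low.

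The permutation check addresses chance only. It does not make the 16 sites representative, so item 1 is needed whatever it shows. The cost is new wording, a short script and a more modest claim. No further data collection is needed to make these changes, though checking the hypotheses at other sites would be later work.

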#### 8.0 Protection of Human Subject Data

*Overview of Risks*- The primary risk in this study is a breach of confidentiality. In the case of Veterans and Veterans' Caregivers, a breach of confidentiality could cause an unauthorized release of protected health information. In the case of VA Employees and ADNA coordinators, a breach in confidentiality could affect their employment. The project staff are aware of these risks and have outlined precautionary measures to reduce this risk as much as possible in the project.

*Data Assurances* - All study staff will be monitored by the [name] and Local Site PIs for consenting, protocol, and information security adherence. Intensive training (including all VHA mandated trainings) at study initialization will be conducted along with annual refresher courses. Training certificates for all study staff members will be kept on file with the PVAMC Research Office. [name] will terminate access to study records when a user no longer requires access to them.

If there is a theft, loss, or other unauthorized access of study data or storage devices associated with this study, this will be reported according to VA regulations. The local ISO/PO will be informed if there is any theft, loss, or other unauthorized access of sensitive data or storage devices and non-compliance with security controls.

## Electronic Health Data/Secondary Data Storage (Obtained through DUAs)

All electronic health data, including all Personal health information and HIPAA identifiers from the secondary data used in objectives 1 and 2 will be stored and accessed exclusively on the Providence VA APP 26 research sever in a restricted access folder limited to

approved project members. Data related to this project containing no PHI or HIPAA identifiers will be stored on the Providence research server on (\\R04pronas21.v01.med.va.gov\RESEARCH\_PROTOCOLS\[name]\VD-HCBS-R, or VHAPROAPP26 H:\Research\_Protocols\_COIN\[name]). Please see section "Description of Providence Research Computing Infrastructure" for further information.

Any paper data generated in connection with this research study will be stored at the Providence VA Medical Center in a restricted access building, in a locked office, in a locked cabinet/drawer. In there is a theft, loss or other unauthorized access of study data or storage devices associated with this study, this will be reported according to VA regulations. All electronic data collected as a part of this study will be stored an analyzed on the Providence VA Research server. Data will only be disseminated in aggregate form and will not include any identifiable information. All records including qualitative interview recordings will be maintained in accordance with the Department of Veterans Affairs record Control Schedule 10-1. Should an inappropriate disclosure of the data occur, the Privacy Officer and ISO will be notified immediately.

## **Qualitative Interview Data Storage:**

There are two types of qualitative interview data to be collected as a part of this project. These are led by separate Investigators and will use different data collection methods.

The list of interview participants for Objective 1 and 3 will be maintained exclusively on the Providence VA server in a folder

(\\R04pronas21.v01.med.va.gov\RESEARCH\_PROTOCOLS\[name]\VD-HCBS-R ) with access restricted to project team members. The Providence VA server complies with all VA Data Security regulations. Only research team members with the proper permissions will have access to this list. Hard copy and electronic interview notes will be labeled only with a coded identification number. The crosswalk of names to identification numbers will be stored in hard copy only in a separate, secure file cabinet in Building 32 on the Providence VAMC campus accessible only to the project team as needed to complete their project duties.

As described above in the methods section and noted in the information consent sheet, interviews will be recorded exclusively for transcription purposes. Veteran Interviews will be conducted by [name] of Boston College a Providence VA IPA employee but recorded by a Providence VA study member also attending the call. All participants will be reminded that they are being recorded and whom is on the call. No name, PHI, PPI or HIPAA identifiers will be collected in these interviews. After obtaining the appropriate permissions and sanctuary to insert the recorder via its USB port to a VA computer, a Providence VA

study member will upload the audio to a restricted file on the protected Providence server (\R04pronas21.v01.med.va.gov\RESEARCH\_PROTOCOLS\[name]\VD-HCBS-R).

Alternatively, if the Providence staff is unavailable to record, the interview will be recorded on the recorder by [name], and [name] will physically claim the recorder and transport it to the Providence VA in a HIPAA compliant locked bag. The interviews will be uploaded as stated above. All recorders will be kept in a locked office in a locked room in both the Providence and Boston locations.

[name] at the Durham VAMC will be conducting the Coordinator/ key informant interviews. An approved digital recording device will be used to audio-record the key informant interviews. No PHI, PPI or HIPAA identifiers will be collected as a part of these interviews. The recordings will be recorded directly into a restricted access folder on the Providence server, or will be recorded onto a VA approved recording device and uploaded immediately to a restricted-use folder on the Providence VAMC server and then deleted from the recording device.

For all transcriptions not completed by a project team member, copies of the files will be accessed by the HSR&D Centralized Transcription Service Program (CTSP), Salt Lake City, UT, one of our local sites. The CTSP is a national VA service, housed behind the VA firewall in the Veterans Health Administration Salt Lake City's (VHASLC) Informatics, Decision-Enhancement and Analytic Sciences (IDEAS 2.0) Center of Innovation (COIN). All leadership and staff are VA employees. All data will reside on the Providence Server and no data will be copied onto the local VA SLC files. Their service is approved by the VA SLC IRB and there is no outside contracting. Data analyses for the qualitative aims will be done using NViVO and/or Atlas software. All records including qualitative interview recordings will be maintained in accordance with the Department of Veterans Affairs record Control Schedule 10-1. Should an inappropriate disclosure of the data occur, the Privacy Officer and ISO will be notified immediately

